### 3. PATIENT SELECTION

#### 3.1 Pre-Registration Eligibility Criteria

3.1.1 Patient has or suspected to have one of the following:

- Newly diagnosed Acute Myeloid Leukemia (AML) associated with antecedent myeloproliferative disorder (Polycythermia Vera, Essential Thrombocythemia, Myelofibrosis, atypical Chronic Myeloid Leukemia, Chronic Myelomonocytic Leukemia and related undifferentiated myeloproliferative/myelodysplastic disorders)
- Relapsed/refractory AML associated with antecedent myeloproliferative disorder (Polycythermia Vera, Essential Thrombocythemia, Myelofibrosis, atypical Chronic Myeloid Leukemia , Chronic Myelomonocytic Leukemia and related undifferentiated myeloproliferative/myelodysplastic disorders) who have received two or fewer prior induction chemotherapy courses
- Accelerated phase myeloproliferative disorders per Zeider et al with two or fewer prior therapies.
  - For aggressive phase MPD (P. Vera, essential thrombocythemia, Ph-negative chronic myelogenous leukemia), one or more of the following criteria must be met: marrow blasts >5%, peripheral blood blasts plus progranulocytes > 10%, new onset or increasing myelofibrosis, new onset or > 25% increase in hepatomegaly or splenomegaly, new onset constitutional symptoms (fever, weight loss, spleni pain, bone pain). Zeider et al
  - For Chronic Myelomonocytic Leukemia (CMML), the following criteria must be met: 5-19% bone marrow blasts (aggressive) or  $\geq$  20% marrow blasts (transformation).

3.1.2 Bone marrow and/or peripheral blood specimens will be submitted for correlative studies as outlined in Section 9. Patients with a dry tap will still be eligible.

### **3.2 Randomization Eligibility Criteria**

3.2.1 Bone marrow aspirate and/or peripheral blood specimens were submitted to the central lab and site has confirmation by the local institution that the patient meets one of the criteria specified in 3.1.1 above.

3.2.2 Age  $\geq 18$  years. Because no dosing or adverse event data are currently available on the use of veliparib in combination with topotecan and carboplatin in patients  $<18$  years of age, children are excluded from this study, but will be eligible for future pediatric trials.

3.2.3 ECOG performance status  $\leq 2$  or Karnofsky  $\geq 60\%$  (see Appendix A).

3.2.4 Patients must have normal organ function as defined below:

- Total bilirubin	less than 2.0 mg/dL unless due to Gilbert's Syndrome, then less than 5.0 mg/dL
- AST(SGOT)/ALT(SGPT)	less than $5 \times$ institutional upper limit of normal
- Creatinine Clearance	GFR greater than 30 ml/min per modified Cockcroft-Gault formula

3.2.5 Interval of greater than 4 weeks since allogeneic blood or marrow transplantation (BMT) if performed; and absence of active GVHD

3.2.6 The effects of veliparib on the developing human fetus are unknown. For this reason and because PARP inhibiting agents as well as topoisomerase inhibitors and platinating agents are known to be teratogenic, women of child-bearing potential must agree to use adequate contraception (hormonal or barrier method of birth control; abstinence) prior to study entry, for the duration of study participation, and for 6 months following the last dose of study drug. Should a woman become pregnant or suspect she is pregnant while she or her partner is participating in this study, she should inform her treating physician immediately. Men treated or enrolled on this protocol must also agree to use adequate contraception prior to the study, for the duration of study participation, and 4 months after completion of veliparib administration.

3.2.7 Ability to understand and the willingness to sign a written informed consent document.

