### **3.3 Exclusion Criteria**

3.3.1 Patients who have had chemotherapy or radiotherapy within 4 weeks prior to entering the study with the exception of hydroxyurea for cytoreduction. Therapy with tyrosine kinase inhibitors (TKIs) directed against JAK2, BCR-ABL or FLT3 will be allowed to be continued until 24 hours prior to start of therapy on trial.

3.3.2 Patients with active uncontrolled infection. Antibiotic therapy for fevers, and continuation of treatment of prior infection are allowed.

- 3.3.3 Patients who have active CNS disease are excluded. Patients with known active CNS leukemia should be excluded from this clinical trial because of their poor prognosis and because they often develop progressive neurologic dysfunction that would confound the evaluation of neurologic and other adverse events.
- 3.3.4 Patients who are receiving any other investigational agents. Patients who have completed therapy with an investigational agent should be off this therapy for at least 5 half-lives or two weeks, whichever is shorter.
- 3.3.5 History of allergic reactions attributed to compounds of similar chemical or biologic composition to veliparib, topotecan or carboplatin.
- 3.3.6 Uncontrolled intercurrent illness including, but not limited to, active infection, symptomatic congestive heart failure, unstable angina pectoris, cardiac arrhythmia, or psychiatric illness/social situations that would limit compliance with study requirements.
- 3.3.7 Pregnant women are excluded from this study because veliparib is PARP inhibiting agent with the potential for teratogenic or abortifacient effects. Because there is an unknown but potential risk for adverse events in nursing infants secondary to treatment of the mother with veliparib, breastfeeding should be discontinued if the mother is treated with veliparib. These potential risks may also apply to topotecan and carboplatin used in this study.
- 3.3.8 HIV-Patients positive patients are not excluded if they have CD4+ cells  $\geq 250/\text{mm}^3$  and negligible viral load and are on a stable combination antiretroviral therapy.
- 3.2.9 History of uncontrolled seizure disorder, including focal or generalized seizure within the past year

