#### **5.4 Duration of Follow Up**

Patients will be followed for *minimum of 30 days, or longer* after removal from protocol treatment or until death, whichever occurs first. Patients removed from study for unacceptable adverse event(s) will be followed until resolution or stabilization of the adverse event.

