## 6. DOSING DELAYS/DOSE MODIFICATIONS

### 6.1 Dosing Delays

Once a cycle is started, prescribed therapy will not be delayed. Patients unable to take veliparib due to toxicity will have those doses skipped.

For patients achieving CR, CRI, PR, or MR following cycle 1, a repeat cycle of the same regimen may be administered beginning no sooner than Day 28 of the preceding cycle and no later than Day 63 from the initiation of the previous cycle (see **Section 5.1**). Delays beyond day 63 should be reviewed with the principal investigator and may be approved if patient is deemed be achieving clinical benefit.

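### Section 3.2.6 starts men's 4-month post-treatment contraception at the end of veliparib, so the period has no start for men in Arm B, who never receive veliparib

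*Combined protocol and SAP*

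**What the plan says.** Section 3.2.6 (Randomization Eligibility Criteria) sets the contraception rules for both sexes in one paragraph.

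- **Reason given.** "PARP inhibiting agents as well as topoisomerase inhibitors and platinating agents are known to be teratogenic". This names the class of veliparib and the classes of both backbone drugs.
- **Women.** Contraception is required before entry, during participation, "and for 6 months following the last dose of study drug".
- **Men, who is covered.** "Men treated or enrolled on this protocol must also agree to use adequate contraception prior to the study". The sentence makes no distinction by arm.
- **Men, how long.** "for the duration of study participation, and 4 months after completion of veliparib administration".

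Sections 5.1 and 13.1 give veliparib to Arm A only (Days 1-21, with topotecan and carboplatin on Days 3-7). Arm B receives topotecan and carboplatin on Days 1-5 and nothing else.

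Section 5.4 sets follow-up after removal from protocol treatment, or until death if sooner, at a "minimum of 30 days, or longer". Section 6.1 adds, for Arm A, "Patients unable to take veliparib due to toxicity will have those doses skipped".

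**The concern.** The men's rule covers both arms, but its clock depends on a drug that one arm never receives. For a man randomised to Arm B, completion of veliparib does not occur, so the 4-month period has no first day and no last day. The plan's own reasoning puts him within the rule, because it names the classes of both drugs he is given. The sentence for women, in the same paragraph, uses an anchor that works in either arm, and the documents give no reason for a different anchor for men.

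This is an eligibility criterion: each man has to agree to it before he knows his arm. If he is then assigned to Arm B, the protocol text gives the site no post-treatment date to tell him. What is at stake is possible fetal exposure through a male patient soon after chemotherapy. No endpoint, analysis or error rate is affected.

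**Working it through.** The plan states no figure to reproduce. The check sets the sections side by side and then sizes the gap.

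**1. Does the men's clock start in each arm?**

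| | Event that starts the clock | Arm A | Arm B |
|---|---|---|---|
| Women, 6 months | last dose of study drug | occurs | occurs |
| Men, 4 months | completion of veliparib | occurs | never occurs |

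**2. Does another section supply a men's period?** None in the supplied text does. Section 3.3.7 says of the risks in pregnancy and nursing that "These potential risks may also apply to topotecan and carboplatin used in this study", but it concerns women. Section 5.2.4 also concerns women. Section 7.5 sets a 90-day window for reporting pregnancies, which is not a contraception duty.

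**3. How many men?** The Planned Enrollment Report lists 29 + 6 = 35 men among 60 patients. Section 13.2 puts 20 patients in Arm B. If the sex mix is the same in both arms (an assumption), 35 x 20/60 = 11.7, about 12 men. If 35 of the 60 are men and chance alone decides the arm, the central 95% range of the hypergeometric distribution is 8 to 15. The documents do not say how many would have a partner who could conceive.

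**4. How large is the shortfall for an Arm B man?** Four consecutive calendar months span 120 to 123 days. The shortfall is that span minus the days from last dose to the end of participation. Participation is not defined, so three readings are shown.

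- *Longest gap.* He is removed from treatment on the day of the last dose and participation ends at the 30-day minimum: 120 - 30 = 90 to 123 - 30 = 93 days short.
- *Intermediate.* He is removed at the recovery assessment on Day 28-42 (section 10; removal at that visit is an assumption) and participation ends 30 days later. It then ends on Day 58 to 72. The last Arm B dose is on Day 5, so this is 58 - 5 = 53 to 72 - 5 = 67 days after it. Shortfall: 120 - 67 = 53 to 123 - 53 = 70 days.
- *No gap.* Follow-up for the 2-year disease-free and overall survival objective (section 1.2) counts as participation. He is then bound beyond 4 months and the shortfall is zero.

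**5. The related Arm A case.** With full dosing, veliparib ends on Day 21 and chemotherapy on Day 7, so the clock starts 21 - 7 = 14 days after chemotherapy and the rule works. If veliparib is last taken on one of Days 1 to 6, and that counts as completion, the clock starts 7 - 1 = 6 to 7 - 6 = 1 day before chemotherapy ends. A last dose on Day 7 gives a difference of zero. A larger difference needs every cycle 2 veliparib dose to be skipped and cycle 2 to be the last. Cycle 2 starts on Day 28 to 63 of the preceding cycle, so its Day 7 falls on Day 34 to 69, and the clock starts 34 - 21 = 13 to 69 - 21 = 48 days early.

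**The case against.** The strongest reply is that Arm B men are not uncovered. They must use contraception before the study and throughout participation, and section 5.4 allows follow-up longer than 30 days. A trial that compares survival at 2 years has to follow patients well past 4 months, and if that counts as participation there is no shortfall. The 90-day figure also mixes two clocks: the 30 days run from removal from treatment, whereas 4 months would run from the last dose. It therefore applies only when the two dates coincide. In addition, 3.2.6 asks a woman who becomes or may be pregnant to act: "while she or her partner is participating in this study, she should inform her treating physician immediately". All of this stands, and it limits the size of the problem. It does not supply the missing start, because participation is undefined and sites would have to choose a reading.

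A second reply is that the consent form or the package inserts, to which section 7.1.2 and sections 8.2 and 8.3 refer sites, may give a date. They cannot be checked here, so the point is confined to the protocol text.

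Some stronger readings are tempting and are not supported:

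- *Arm B men have no contraception duty.* They have one during participation. What is missing is a defined period after treatment.
- *The higher topotecan dose in Arm B makes the gap more dangerous.* The documents do not link dose to contraception length or to risk through the father.
- *The 90-day window in section 7.5 is part of the same error.* It is a reporting rule, and nothing requires it to match the contraception period.
- *The rule fails generally in Arm A.* It fails only when veliparib stops before chemotherapy does, and skipped doses need not count as completion of veliparib.

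**Conclusion.** The point holds as a wording error in 3.2.6. As written, the men's 4-month post-treatment period cannot be applied in Arm B, although the paragraph's stated reason covers both Arm B drugs and the women's sentence avoids the problem.

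It would affect about 12 men (8 to 15 by chance), assuming the planned sex mix. Against 4 months, the shortfall runs from none to about 90 days, depending on what participation means and when treatment is declared over. A reader might infer that every Arm B man is some 90 days short. The documents do not support that, because 90 days is the end of the range and needs two unfavourable assumptions together. The Arm A case is minor: 1 to 6 days within a single cycle, and more only under the cycle 2 assumption.

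The correction should be made because it is small and concerns a safety instruction that men in one arm cannot apply as written.

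**What to change.** In section 3.2.6, end the men's sentence with: *4 months after the last dose of any study drug (veliparib, topotecan or carboplatin)*. This uses the same kind of anchor as the women's rule, works in both arms, and removes the Arm A edge case. For an Arm A man the new date is never earlier than the present one.

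The 4 months is the plan's own figure, and the documents give no basis for it with topotecan and carboplatin alone. The sponsor should confirm the length against the two labels and make the consent form match.

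The cost is one phrase at the next amendment, with no added visit or procedure. The downside is a fixed 4-month duty for Arm B men where the text now sets none.

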### **3.3 Exclusion Criteria**

3.3.1 Patients who have had chemotherapy or radiotherapy within 4 weeks prior to entering the study with the exception of hydroxyurea for cytoreduction. Therapy with tyrosine kinase inhibitors (TKIs) directed against JAK2, BCR-ABL or FLT3 will be allowed to be continued until 24 hours prior to start of therapy on trial.

3.3.2 Patients with active uncontrolled infection. Antibiotic therapy for fevers, and continuation of treatment of prior infection are allowed.

- 3.3.3 Patients who have active CNS disease are excluded. Patients with known active CNS leukemia should be excluded from this clinical trial because of their poor prognosis and because they often develop progressive neurologic dysfunction that would confound the evaluation of neurologic and other adverse events.
- 3.3.4 Patients who are receiving any other investigational agents. Patients who have completed therapy with an investigational agent should be off this therapy for at least 5 half-lives or two weeks, whichever is shorter.
- 3.3.5 History of allergic reactions attributed to compounds of similar chemical or biologic composition to veliparib, topotecan or carboplatin.
- 3.3.6 Uncontrolled intercurrent illness including, but not limited to, active infection, symptomatic congestive heart failure, unstable angina pectoris, cardiac arrhythmia, or psychiatric illness/social situations that would limit compliance with study requirements.
- 3.3.7 Pregnant women are excluded from this study because veliparib is PARP inhibiting agent with the potential for teratogenic or abortifacient effects. Because there is an unknown but potential risk for adverse events in nursing infants secondary to treatment of the mother with veliparib, breastfeeding should be discontinued if the mother is treated with veliparib. These potential risks may also apply to topotecan and carboplatin used in this study.
- 3.3.8 HIV-Patients positive patients are not excluded if they have CD4+ cells  $\geq 250/\text{mm}^3$  and negligible viral load and are on a stable combination antiretroviral therapy.
- 3.2.9 History of uncontrolled seizure disorder, including focal or generalized seizure within the past year

#### **3.4 Inclusion of Women and Minorities**

NIH policy requires that women and members of minority groups and their subpopulations be included in all NIH-supported biomedical and behavioral research projects involving NIH-defined clinical research unless a clear and compelling rationale and justification establishes to the satisfaction of the funding Institute & Center (IC) Director that inclusion is inappropriate with respect to the health of the subjects or the purpose of the research. Exclusion under other circumstances must be designated by the Director, NIH, upon the recommendation of an IC Director based on a compelling rationale and justification. Cost is not an acceptable reason for exclusion except when the study would duplicate data from other sources. Women of childbearing potential should not be routinely excluded from participation in clinical research. Please see <http://grants.nih.gov/grants/funding/phs398/phs398.pdf>.

## 4. REGISTRATION PROCEDURES

### 4.1 Investigator and Research Associate Registration with CTEP

Food and Drug Administration (FDA) regulations and National Cancer Institute (NCI) policy require all individuals contributing to NCI-sponsored trials to register and to renew their registration annually. To register, all individuals must obtain a Cancer Therapy Evaluation Program (CTEP) Identity and Access Management (IAM) account at <https://ctepcore.nci.nih.gov/iam>. In addition, persons with a registration type of Investigator (IVR), Non-Physician Investigator (NPIVR), or Associate Plus (AP) (*i.e.*, clinical site staff requiring write access to Oncology Patient Enrollment Network (OPEN), Rave, or acting as a primary site contact) must complete their annual registration using CTEP's web-based Registration and Credential Repository (RCR) at <https://ctepcore.nci.nih.gov/rcr>.

RCR utilizes five person registration types.

- IVR: MD, DO, or international equivalent,
- NPIVR: advanced practice providers (e.g., NP or PA) or graduate level researchers (e.g., PhD),
- AP: clinical site staff (e.g., RN or CRA) with data entry access to CTSU applications (e.g., Roster Update Management System [RUMS], OPEN, Rave,),
- Associate (A): other clinical site staff involved in the conduct of NCI-sponsored trials, and
- Associate Basic (AB): individuals (e.g., pharmaceutical company employees) with limited access to NCI-supported systems.

RCR requires the following registration documents:

Documentation Required	IVR	NPIVR	AP	A	AB
FDA Form 1572	✓	✓			
Financial Disclosure Form	✓	✓	✓		
NCI Biosketch (education, training, employment, license, and certification)	✓	✓	✓		
GCP training	✓	✓	✓		
Agent Shipment Form (if applicable)	✓				
CV (optional)	✓	✓	✓		

An active CTEP-IAM user account and appropriate RCR registration is required to access all CTEP and Cancer Trials Support Unit (CTSU) websites and applications. In addition, IVRs and NPIVRs must list all clinical practice sites and Institutional Review Boards (IRBs) covering their practice sites on the FDA Form 1572 in RCR to allow the following:

- Addition to a site roster,
- Assign the treating, credit, consenting, or drug shipment (IVR only) tasks in OPEN,
- Act as the site-protocol Principal Investigator (PI) on the IRB approval, and
- Assign the Clinical Investigator (CI) role on the Delegation of Tasks Log (DTL).

In addition, all investigators act as the Site-Protocol PI, consenting/treating/drug shipment, or as the CI on the DTL must be rostered at the enrolling site with a participating organization (*i.e.*, Alliance).

Additional information is located on the CTEP website at <https://ctep.cancer.gov/investigatorResources/default.htm>. For questions, please contact the **RCR Help Desk** by email at [[contact]](mailto:[contact]).

## 4.2 Site Registration

This study is supported by the NCI Cancer Trials Support Unit (CTSU).

### IRB Approval

Sites participating with the NCI Central Institutional Review Board (NCI CIRB) must submit the Study Specific Worksheet for Local Context (SSW) to the CIRB using IRBManager to indicate their intent to open the study locally. The NCI CIRB's approval of the SSW is automatically communicated to the CTSU Regulatory Office, but sites are required to contact the CTSU Regulatory Office at [[contact]](mailto:[contact]) to establish site preferences for applying NCI CIRB approvals across their Signatory Network. Site preferences can be set at the network or protocol level. Questions about establishing site preferences can be addressed to the CTSU Regulatory Office by emailing the email address above or calling [name].

***For trials that will include sites using their local IRB or REB as well as for a trial with non-U.S.-based NCTN and NCORP sites, include the following paragraph and the three associated bullet points:***

Sites using their local IRB or REB must submit their approval to the CTSU Regulatory Office using the Regulatory Submission Portal located in the Regulatory section of the CTSU website. Acceptable documentation of local IRB/REB approval includes:

- Local IRB documentation,
- IRB-signed CTSU IRB Certification Form, and/or
- Protocol of Human Subjects Assurance Identification/IRB Certification/Declaration of Exemption Form.

In addition, the Site-Protocol PI (*i.e.*, the investigator on the IRB/REB approval) must meet the following five criteria to complete processing of the IRB/REB approval record:

- Holds an Active CTEP status,
- Rostered at the site on the IRB/REB approval (*applies to US and Canadian sites only*) and on at least one participating roster,
- If using NCI CIRB, rostered on the NCI CIRB Signatory record,
- Includes the IRB number of the IRB providing approval in the Form FDA 1572 in the RCR profile, and
- Holds the appropriate CTEP registration type for the protocol.

## **Additional Requirements**

Additional requirements to obtain an approved site registration status include:

- An active Federalwide Assurance (FWA) number,
- An active roster affiliation with the Lead Protocol Organization (LPO) or a Participating Organization, and
- Compliance with all protocol-specific requirements (PSRs).

### **4.2.1 Downloading Regulatory Documents**

Download the site registration forms from the protocol-specific page located on the CTSU members' website. Permission to view and download this protocol and its supporting documents is restricted based on person and site roster assignment. To participate, the institution and its associated investigators and staff must be associated with the LPO or a Participating Organization on the protocol.

- Log on to the CTSU members' website (<https://www.ctsu.org>) using your CTEP-IAM username and password,
- Click on *Protocols* in the upper left of your screen
  - Enter the protocol number in the search field at the top of the protocol tree, or
  - Click on the By Lead Organization folder to expand, then select LAO-MD017, and protocol number 10147,
- Click on *Documents*, select *Site Registration*, and download and complete the forms provided. (Note: For sites under the CIRB initiative, IRB data will load automatically to the CTSU as described above.)

